3.2. Study Endpoints

3.2.1. Primary Endpoint (powered):

- Reduction in severity of MR at 30 days of at least one category on a 0-4 scale.

3.2.2. Key Secondary Endpoint (powered):

- Change in 6 minute walk test at 6 months

3.2.3. Secondary Endpoints (all at 6, 12, and 24 months except as indicated) :

- Key Secondary Endpoint (powered): Change in 6 minute walk test at 6 months.
- Secondary Endpoints (all at 6, 12, and 24 months except as indicated) :
 - 1) MR severity
 - 2) 6 minute walk distance
 - 3) Quality of life as assessed by the Kansas City Cardiomyopathy Questionnaire (KCCQ) (also at 30 days)
 - 4) NYHA Class (also at 30 days)
 - 5) Left Ventricular End Diastolic Volume (LVEDV)
 - 6) Left Ventricular End Systolic Volume (LVESV)
 - 7) Device success defined as deployment of the Cardioband, with MR reduction at hospital discharge.
 - 8) Individual patient success (6 months and 1 year) defined as device success and the following:
 - 9) Discharged from index hospitalization
 - 10) NYHA class improvement by at least 1 level from baseline
 - 11) Days alive and out of hospital (due to major cardiovascular events) at 1 year
 - 12) Freedom from all-cause mortality and major adverse events defined as disabling stroke, myocardial infarction (peri-procedural or spontaneous), renal failure requiring dialysis, life-threatening bleeding, cardiac tamponade, and device related cardiac surgical intervention

	REPAIR - Transcatheter REPAIR of Mitral Insufficiency with CaRdioband System Post Market Study Protocol ID CB1-3	
---	---	---

at 30 days from the implant procedure or hospital discharge, whichever is later. (Individual components will also be evaluated).

- 13) Need for urgent/emergent surgical intervention

3.3. Inclusion/Exclusion

[figure not shown]
[figure not shown]
The Principal Investigator will determine the patient's suitability for Cardioband implantation, based on the following inclusion/exclusion criteria:

3.3.1. Inclusion Criteria:

- 1) Age ≥ 18 years
- 2) Severe (3+ to 4+) secondary Mitral Regurgitation
- 3) Symptomatic heart failure (NYHA Class III-IVa) despite guideline directed medical therapy including CRT if indicated
- 4) The Local Site Heart Team concur that surgery will not be offered as a treatment option and that medical therapy is the intended therapy.
- 5) Transfemoral access and transeptal deployment of the Cardioband is determined to be feasible
- 6) Subject is willing and able to provide informed consent and follow protocol

3.3.2. Exclusion Criteria:

- 1) EF < 20%
- 2) LVEDD ≥ 70 mm
- 3) Heavily calcified annulus or leaflets
- 4) Significant CAD requiring revascularization
- 5) Active bacterial endocarditis
- 6) Any percutaneous coronary, carotid, endovascular intervention or carotid surgery within 30 days or any coronary or endovascular surgery within 3 months
- 7) Renal insufficiency requiring dialysis
- 8) Life expectancy of less than twelve months
- 9) Subject is participating in concomitant research studies of investigational products that have not reached their primary endpoint
- 10) Pulmonary hypertension ≥ 70 mmHg at rest
- 11) Mitral valve anatomy which may preclude proper device treatment
- 12) Right-sided congestive heart failure with echocardiographic evidence of severe right ventricular dysfunction and/or severe tricuspid regurgitation
- 13) Severe liver disease
- 14) Patient is pregnant or lactating
- 15) Hypersensitivity to Nickel or Chromium
- 16) Clinically significant bleeding diathesis or coagulopathy

	REPAIR - Transcatheter REPAIR of Mitral Insufficiency with Cardioband System Post Market Study Protocol ID CB1-3	
---	---	---

- 17) History of mitral valve repair
- 18) TIA or CVA within the past 3 months
- 19) Subjects in whom transesophageal echocardiography is contraindicated
- 20) Patients who cannot tolerate anticoagulation/antiplatelet regimen
- 21) Patients with known severe reaction to contrast agents that cannot be adequately premedicated

4. Data collection

Patients will be recruited from the pool of patients who are referred for transcatheter mitral valve repair.

4.1. Key Pre-Implantation Procedures:

- 1. History and Physical
 - 2. TTE , TEE and/or CT
 - 3. 6 minute walk test
 - 4. KCCQ
- 

4.2. Key Post-Procedure Procedures:

- 1. Serial AE assessment, history, and physical at 30 days, 6 months, 12 months, 24 months)
 - 2. Serial TTEs (30 days, 6 months, 12 months, 24 months)
 - 3. 6 minute walk tests (30 days, 6 months, 12 months, 24 months)
 - 4. KCCQ (30 days, 6 months, 12 months, 24 months)
- 

[figure not shown]

5. STUDY VISITS AND PROCEDURES

The study will commence following institutional medical ethics committee

Screening of patients will be performed according to the hospital standard screening for transcatheter mitral valve repair and replacement. Patients will give a written consent for health information release prior to screening process. The treatment procedure will be performed according to the instructions outlined in the current approved IFU. The clinical assessments will be done as per routine practice at the participating sites.

Data will be collected at the following time points (as expected in the course of a normal treatment): baseline, procedure, discharge, clinical follow-up at 30 days, 6 months, 12 months, and 24 months from the index procedure. Data from any other additional time points may be collected and analyzed if available.

	REPAIR - Transcatheter REPair of Mitral Insufficiency with CaRdioband System Post Market Study Protocol ID CB1-3	
---	---	---

The procedures associated with each study visit are outlined and summarized in Table 1.

[figure not shown]

Table 1. Variables captured in the REPAIR database at various time points.

Procedure	Screening	Baseline	Implantation	Discharge	30 days	6 months	12 months	24 months
Visit Number	-1	1	2	3	4	5	6	8
Range	-1 month	-1 month	0	NA	-1 wk/+ 2 wks	+/- 1 month	+/- 1 month	+/- 1 month
Data release Consent	X							
Study informed consent		X						
Demographics		X						
Wearable data watch		X	X	X	X	X	X	X
Medical History		X						
Routine Blood tests		X		X	X	X	X	X
General Clinical State		X		X	X	X	X	X
Adverse Events		X	X	X	X	X	X	X
Medication Profile		X		X	X	X	X	X
Mitral Regurgitation Assessment by TTE	X	X		X	X	X	X	X
Mitral Regurgitation Assessment by TEE		X	X					
Mitral valve anatomy (by Echo and/or CT)	X							
Coronary Angiography (within the past 12 months, optional)	X							
6-minute walk test		X			X	X	X	X
QoL questionnaire (KCCQ)		X			X	X	X	X
NYHA Functional Class		X			X	X	X	X
Cardioband Implantation			X					

	REPAIR - Transcatheter REPAIR of Mitral Insufficiency with Cardioband System Post Market Study Protocol ID CB1-3	
---	---	---

5.1. Echocardiographic imaging

Echocardiographic data will be collected from the TEE and TTE images for the corelab interpretation of the degree of MR reduction and adverse events, if any. A physician or sonographer familiar with valvular heart disease and experienced in performing echocardiograms should perform each assessment.

5.2. Unscheduled Visits

An unscheduled visit will be any visit to the clinical site other than the specific visits requested in the protocol. The Investigator or trained and qualified staff will perform all procedures necessary to evaluate the study participant at these visits, and record the visit in the subject's chart. The Principal Investigator must be notified by the subject immediately of any unscheduled visits to any medical facilities during the study period. (Subjects will be instructed to report).

6. STATISTICAL ANALYSIS & DATA MANAGEMENT

6.1 Number of patients (sample-size)

Based on the results of the Cardioband CE mark study (Protocol ID CB 1-2), the present study with a sample size of 50 subjects will have greater than 80% power to detect a reduction in MR severity of at least one grade (CE mark study showed improvement in MR severity of at least one grade in >80% of subjects in CE mark study).

Based on the results of the Cardioband CE mark study (Protocol ID CB 1-2), the present study with a sample size of 50 subjects will have greater than 90% power to detect an improvement of 75 m in 6 minute walk test at 6 months

The PMS population may be expanded to collect additional experience from market introduction. This will also allow avoiding the potential influence of patients lost to follow-up or withdrawn.

	REPAIR - Transcatheter REPAIR of Mitral Insufficiency with Cardioband System Post Market Study Protocol ID CB1-3	
---	---	---

[figure not shown]
6.2 Statistical rationale

6.2.1 Population: All patients Per Protocol

Endpoint: MR Reduction at 30 days

Estimates:

- Power: 80%, 90%
- Change in MR at 30 Days: 81.48%
- Two-tailed Alpha = 0.05
- Test: Exact Test
- Drop-out rate = 5%

[figure not shown]

6.2.2 Population: All patients Per Protocol

Endpoint: Mean 6MW at 6 Months

Estimates:

- Power: 80%, 90%
- Mean 6Mw at 6 months: 50, 75 meters
- Standard Deviation = 139
- Treatment arms = 1
- Two-tailed Alpha = 0.05
- Test: One-sample t-test
- Drop-out rate = 10%

	REPAIR - Transcatheter REPAIR of Mitral Insufficiency with Carotiband System Post Market Study Protocol ID CB1-3	
---	---	---

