	
 • Discharged from index hospitalization • NYHA class improvement by at least 1 level from baseline 
9) Days alive and out of hospital (due to major cardiovascular events) at 1 year
 
10) Freedom from all-cause mortality and major adverse events defined as disabling stroke, myocardial infarction (peri-procedural or spontaneous), renal failure requiring dialysis, life-threatening bleeding, cardiac tamponade and device related cardiac surgical intervention at 30 days from the implant procedure or hospital discharge, whichever is later. (Individual components will also be evaluated).
 
11) Need for urgent/emergent surgical intervention

Sample Size Considerations	
Based on the results of the Cardioband CE mark study (Protocol ID CB 1-2), the present study with a sample size of 50 subjects will have greater than 80% power to detect a reduction in MR severity of at least one grade (CE mark study showed improvement in MR severity of at least one grade in >80% of subjects in CE mark study).
 
Based on the results of the Cardioband CE mark study (Protocol ID CB 1-2), the present study with a sample size of 50 subjects will have greater than 90% power to detect an improvement of 75 m in 6 minute walk test at 6 months (CE Mark study showed an improvement of 93.3 m ± 90.3 m).

Inclusion Criteria	
 1) Age ≥18 years 2) Severe (3+ to 4+) secondary Mitral Regurgitation 3) Symptomatic heart failure (NYHA Class III-IVa) despite guideline directed medical therapy including CRT if indicated 4) The Local Site Heart Team concur that surgery will not be offered as a treatment option and that medical therapy is the intended therapy. 5) Transfemoral access and transseptal deployment of the Cardioband is determined to be feasible 6) Subject is willing and able to provide informed consent and follow protocol
Exclusion Criteria	
 1) EF < 20% 2) LVEDD ≥ 70 mm 3) Heavily calcified annulus or leaflets 4) Significant CAD requiring revascularization 5) Active bacterial endocarditis 6) Any percutaneous coronary, carotid, endovascular intervention or carotid surgery within 30 days or any coronary or endovascular surgery within 3 months 7) Renal insufficiency requiring dialysis

	REPAIR - Transcatheter REPAIR of Mitral Insufficiency with CaRdioband System Post Market Study Protocol ID CB1-3	
---	---	---

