3. STUDY DESIGN

3.1. Overview

The purpose of this PMS is to collect patient data related to mitral valve performance and safety outcomes in patients with severe functional mitral regurgitation (MR) in whom Cardioband will be implanted.

Subjects will be followed for up to 2 years,

A multi-center (up to 20 sites), single arm, open label study in a minimum of 50 subjects. Patients must have provided written consent that their data can be used in the study. The patients will be followed up for 2 years with the primary endpoint being at 6 months.

The study will enrol Patients with secondary (functional) MR, symptomatic (NYHA Class III-IVa heart failure symptoms), with severe MR and to whom The Local Site Heart Team concur that surgery will not be offered as a treatment option. Anatomical feasibility is assessed by Echocardiography and/or other exams (such as CT and angiography) according to the site common practice. The subjects will be screened and enrolled according to the study inclusion and exclusion criteria.

Patients will undergo mitral valve repair with Cardioband implanted via transcatheter procedure under Transesophageal echocardiography (TEE) and fluoroscopy guidance. Post-procedure clinical care will be performed according to standard management of mitral valve repair and Transthoracic Echo (TTE) assessment of the degree of mitral regurgitation will be obtained at hospital discharge, 30 days, 6, 12 and 24 months post-index procedure.

	REPAIR - Transcatheter REPAIR of Mitral Insufficiency with CaRdioband System Post Market Study Protocol ID CB1-3	
---	---	---

Transthoracic Echocardiography (TTE) performed by the Study clinical sites will be used for sequential assessments of mitral regurgitation at baseline, at discharge and during follow-up. Guidelines for recording the echocardiographic examination of mitral regurgitation will be provided to the sites. An echocardiographic Core Lab will be involved in assessing echocardiographic examinations. 

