6.3.2 Procedures for handling withdrawal

Subjects who withdraw or are withdrawn from the study should:

- Have the reason(s) for their withdrawal recorded (if possible).
- May be seen by an investigator and all final assessments should be performed and recorded.
- Be asked about the presence of any AEs. If an ongoing AE is present, the patient should be followed up until satisfactory clinical resolution of the event is achieved.

If a subject is withdrawn, Valtech monitor should be informed as soon as possible by the site. One additional subject will be enrolled for each subject withdrawn (or died) for any reason before the primary endpoint period completed.

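### Does the unexplained SD of 139 m for the 6-minute walk endpoint in section 6.2.2 undermine the power claim?

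*Combined protocol and SAP*

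**What the plan says.** The key secondary endpoint in section 3.2.2 is "Change in 6 minute walk test at 6 months", and the synopsis words it the same way. Section 6.1 states that 50 subjects give "greater than 90% power to detect an improvement of 75 m in 6 minute walk test at 6 months". The synopsis makes the same claim and adds that the "CE Mark study showed an improvement of 93.3 m ± 90.3 m".

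Section 6.2.2 lists the planning inputs: "Endpoint: Mean 6MW at 6 Months", effects of 50 and 75 m, "Standard Deviation = 139", "Test: One-sample t-test", two-sided alpha of 0.05, power of 80% and 90%, one arm and 10% drop-out. It does not say where 139 comes from, how it relates to 90.3, or what the null value is.

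**The concern.** There are two apparent faults. First, the label in section 6.2.2 reads as a walk distance measured at 6 months, whereas the endpoint is a change from baseline. A one-sample t-test on change needs the SD of the change, and the SD of a distance is a different quantity. Second, the power statement is said to rest on the CE-mark study. The only 6-minute walk spread visible for that study is 90.3 m, yet the planning section uses a figure 139/90.3 = 1.54 times as large.

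If the wrong SD had been used in the optimistic direction, the power for the key secondary endpoint would be overstated. The SD also governs how many 6-month walk tests can be lost before power falls below 90%. That margin seems to matter because replacement of lost subjects ("One additional subject will be enrolled for each subject withdrawn (or died) for any reason before the primary endpoint period completed") depends on when the primary endpoint period ends. Section 3.2.1 puts the primary endpoint at 30 days, while section 3.1 says "The patients will be followed up for 2 years with the primary endpoint being at 6 months".

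**Working it through.** **Inputs.** Effect 75 m, SD 139 m, two-sided alpha 0.05, one-sample t-test and 10% drop-out come from section 6.2.2. n = 50 and the claim of more than 90% come from section 6.1. The alternative SD of 90.3 m comes from the synopsis, with the unlabelled ± term assumed to be an SD. The null is not stated, so zero change is assumed.

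**Formula.** Noncentrality = (effect / SD) × √n, with n − 1 degrees of freedom. Power is the probability that the noncentral t exceeds the two-sided 5% critical value. Evaluable subjects after drop-out: 50 × 0.90 = 45.

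**The plan's own figure, SD 139.**
- n = 50: (75/139) × √50 = 0.540 × 7.071 = 3.82, power 0.962.
- n = 45: 0.540 × 6.708 = 3.62, power 0.943.
- Smallest n for 90%: n = 38 gives 0.8995 and n = 39 gives 0.907, so 39 evaluable. Allowing for drop-out, 39/0.90 = 43.3, or 44 enrolled, which is below 50.

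The stated power of more than 90% is reproduced, with and without drop-out.

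**With SD 90.3 instead.**
- n = 50: (75/90.3) × √50 = 0.831 × 7.071 = 5.87, power 0.9999.
- n = 45: 0.831 × 6.708 = 5.57, power 0.9998.
- Smallest n for 90%: 18 evaluable, or 18/0.90 = 20 enrolled.

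| SD (m) | Power, n = 50 | Power, n = 45 | Evaluable needed for 90% | Losses tolerated from 50 |
|---|---|---|---|---|
| 139 | 0.962 | 0.943 | 39 | 11 (22%) |
| 90.3 | 0.9999 | 0.9998 | 18 | 32 (64%) |

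**Room for error in the SD.** Power for 75 m stays above 90% for any SD of change up to about 160 m at n = 50 and about 152 m at n = 45. Both figures in the documents lie inside that range.

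**The null value.** Testing against 75 m with a true change of 93.3 m would give power of only 29% (SD 90.3) or 15% (SD 139) at n = 50. Zero change reproduces the claim, so it is the natural reading.

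**Loss margin.** The planned 10% drop-out is 50 × 0.10 = 5 subjects. Either margin, 11 or 32, exceeds 5.

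**The case for a change.** The strongest case for acting is that the label leaves open what 139 measures. If it is the SD of the walk distance, then with equal SDs at both visits and correlation r the SD of change is 139 × √(2(1 − r)). At r = 0.3 that is 164.5 m and power at n = 50 falls to 0.885. Setting the SD of change to 160.4 m, the limit for 90% power at n = 50, gives r = 1 − (160.4/139)²/2 = 0.33. At n = 45, with a limit of 151.8 m, r = 0.40. So this reading could in principle break the claim.

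It does not do so on the evidence in the documents. The only visible spread for the change is 90.3 m, which on this reading implies r = 1 − 90.3²/(2 × 139²) = 0.79 and power above 99.9%. No section gives a baseline SD or a correlation, so the low-correlation scenario is conjecture.

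A second argument is that section 6.2.2 also lists 50 m, where SD 139 gives only 70% power at n = 50 and 66% at n = 45. That is true, but no section promises 50 m with 50 subjects; the claim is for 75 m alone.

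The loss-margin argument is weak. Both margins exceed the planned drop-out, section 3.1 sets 50 as a minimum, and section 6.1 allows the population to be expanded, partly to offset losses. The conflict over the timing of the primary endpoint is real, but it is a separate matter and does not depend on this SD.

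Two editorial points stand: the label should speak of change, and the origin of 139 is not given in the visible text. The body of section 2.4, the summary of clinical results, is missing from the public text and may supply that origin, so its absence cannot be held against the plan.

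**Conclusion.** No change follows. The label in section 6.2.2 is a clerical slip that is unlikely to mislead an analyst: sections 3.2.2 and 6.1 speak of change and improvement, and 50 or 75 m makes sense only as a change. A planning SD that differs from an earlier study's reported SD is not a contradiction. The planned effects also differ from the CE-mark mean of 93.3 m, so the plan evidently did not carry over the earlier results unaltered. The section states which SD it used, and of the two it is the cautious one.

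The stated power of more than 90% for 75 m with n = 50 holds at 96% (94% after 10% drop-out) with SD 139 m, and above 99.9% with SD 90.3 m. An analyst following the plan would run the same test on the same number of subjects whichever SD is taken. The conclusion assumes that ±90.3 is an SD, that the null is zero change, and that the true SD of change is no more than about 152 m if 45 subjects are evaluable.

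### The MR and 6-minute walk tests each carry the full two-tailed 0.05, and no readable rule makes the walk claim depend on the MR result

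*Combined protocol and SAP*

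**What the plan says.** Section 3.2 names MR reduction of at least one category at 30 days as the powered primary endpoint. It then lists "Key Secondary Endpoint (powered): - Change in 6 minute walk test at 6 months". The synopsis has a separate hypothesis for each, and a third for quality of life.

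Section 6.2.1 plans the MR endpoint with "Change in MR at 30 Days: 81.48" per cent, "Test: Exact Test", "Drop-out rate = 5" per cent and a two-tailed 0.05. Section 6.2.2 plans the walk endpoint with a one-sample t-test, SD 139 m, 10% drop-out and again "Two-tailed Alpha = 0.05". Section 6.1 claims "greater than 90% power to detect an improvement of 75 m in 6 minute walk test at 6 months" for 50 subjects, without reference to the MR result.

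No readable text gives a testing order, an alpha split or a definition of study success, and the table of contents lists no multiplicity section. Section 3.1 describes follow-up of 2 years "with the primary endpoint being at 6 months", which conflicts with the 30 days in 3.2.1.

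**The concern.** Calling one endpoint primary and the other key secondary ranks their importance. It does not say what happens to the second test when the first one misses. As the plan reads, a study that fails on MR could still report a significant walk improvement at the full 0.05. The 5% error rate then holds for each test but not for the pair.

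This matters more here than in a controlled trial. The study is single-arm and open-label, and walk distance depends on effort, so a before-after gain can appear without a device effect. A rule fixed in advance removes the choice of which result to lead with. The two statements of when the primary endpoint falls make the intended order less clear, because 6 months is also the walk test's time point.

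**Working it through.** **Inputs.** Two-tailed alpha 0.05 for each test (6.2.1, 6.2.2); N = 50 (6.1); walk 75 m, SD 139 m, 10% drop-out, so 50 × 0.90 = 45 evaluable (6.2.2); true MR response 81.48%, 5% drop-out, so 50 × 0.95 = 47.5, i.e. 47 or 48 evaluable (6.2.1). The readable text gives no null rate for MR and no correlation between the tests; both are assumed and shown as ranges.

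**1. The plan's own power figures.** For the walk test the noncentrality is (75/139) × √n. At n = 50 it is 3.82 (critical t 2.01), giving power 96.2%; at n = 45 it is 3.62 (critical t 2.02), giving 94.3%. The stated figure of more than 90% is reproduced. The MR power cannot be reproduced without the null rate. The stated figure of more than 80% would hold for assumed nulls up to about 61.5-62.5% with 47-50 evaluable.

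**2. Nominal error for the pair, both nulls true, independent tests.**
- Two-sided: 1 − 0.95² = 9.75%, against 5% for one test (upper limit under any dependence: 0.05 + 0.05 = 10%).
- Favourable direction only: 1 − 0.975² = 4.94%, against 2.5%.

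**3. Allowing for the exact test.** A discrete test seldom uses its full 0.05. With actual size s (at most 2.5% in each tail), the pair's error is 1 − (1 − s) × 0.95. Assumed nulls run from 50% to 70% in steps of 5 points, at n = 47, 48 and 50.
- Example, n = 50, null 60%: success needs 38/50; upper tail 1.33%, lower tail 1.60%, s = 2.93%. Pair: 1 − 0.9707 × 0.95 = 7.8%. Favourable: 1 − 0.9867 × 0.975 = 3.8%.
- Lowest two-sided (n = 48, null 70%): s = 2.60%, pair 7.5%.
- Highest two-sided (n = 48, null 65%): s = 4.80%, pair 9.6%.
- Favourable direction over the same grid: 3.6% to 4.9%.

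**4. Allowing for correlation** (bivariate normal, ignoring discreteness). At r = 0.3, 0.5 and 0.8 the two-sided rate is 9.5%, 9.1% and 7.8%; the favourable-direction rate is 4.8%, 4.5% and 3.9%.

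**5. Under a fixed sequence.** If the MR null is true, any error requires a significant MR result. If only the walk null is true, any error requires a significant walk result. Either way the family-wise rate is at most 5% two-sided and 2.5% favourable.

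**6. What the sequence costs.** The chance of reaching a walk claim is MR power × walk power, if the tests are independent:

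| MR assumption | MR power, n = 50 / 47 | Walk power, n = 50 / 45 | Product |
|---|---|---|---|
| null 50% | 99.7% / 99.7% | 96.2% / 94.3% | 96% / 94% |
| null 55% | 98.4% / 98.1% | 96.2% / 94.3% | 95% / 92% |
| null 60% | 87.9% / 85.3% | 96.2% / 94.3% | 85% / 80% |
| MR power only 80% | 80% | 96.2% / 94.3% | 77% / 75% |

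**The case against.** The strongest reply is that the alpha entries are sample-size inputs, listed beside power, SD and drop-out, and are not decision rules. A fixed-sequence design would enter 0.05 for both tests too. There is one primary and one key secondary endpoint, they are ranked, and they are read in time order. The study is a post-market data collection with no stated success criterion or labelling claim. This stands to the extent that the defect is an omission: the entries are compatible with a hierarchy, but they do not establish one.

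A reader might infer three stronger things that the documents do not support.
- **That the error rate in practice nearly doubles.** The figure of 9.75% needs both nulls true, independent tests, harmful-direction rejections counted as errors, and a continuous MR test. Section 6.2.1 specifies an exact test, and if only one null is true the pair's error does not exceed 5% anyway.
- **That a walk claim after a missed MR test would be a benefit without the effect meant to produce it.** The MR test compares a responder proportion with a null that cannot be read. With an assumed null of 60% and n = 50, a result of 37/50 would miss although 74% of patients improved by at least one grade.
- **That gating costs almost nothing.** Section 6.1 promises only more than 80% power for MR, and at 80% the chance of a walk claim falls to about 75-77%.

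Figures are missing directly after 6.1 and 6.2.1. A rule stated there cannot be ruled out; if one exists, the sponsor need only point to it.

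**Conclusion.** The point holds as an omission that is worth correcting. Two endpoints labelled powered each have the full two-tailed 0.05, and no readable rule ties the walk claim to the MR result. The primary test on its own is not inflated.

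The problem is confined to the pair when both nulls are true. The error is then at most 9.75% two-sided for independent tests, about 7.5-9.6% once the exact test's discreteness is allowed for, and about 3.6-4.9% in the favourable direction against 2.5%. These figures rest on assumed MR nulls of 50-70%, 47 to 50 evaluable subjects and independence; positive correlation lowers them. Because the remedy needs no patients and follows the sponsor's own ranking, it should be made, but the omission does not undermine the primary analysis.

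**What to change.** - **Section 6.2:** state that MR response at 30 days is tested first at two-sided 0.05. The 6-month walk change is tested at two-sided 0.05 only if MR is significant in the favourable direction; otherwise it is reported as an estimate with a 95% confidence interval and no formal claim.
- **Section 6.2.1:** make sure the MR null rate is stated in the text if it appears only in a figure, since the gate needs a criterion.
- **Sections 3.1 and 3.2.1:** reconcile 6 months with 30 days, so that it is clear which result comes first.
- **Section 6.1:** describe the power of more than 90% as that of the walk test given that the primary has succeeded.
- **Quality of life:** if the third hypothesis is also to support a formal claim, place it as a third step.

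This takes a few sentences and leaves N and both alphas unchanged. The downside is that the formal walk claim is lost if MR fails. The chance of reaching it is about 92-96% for assumed MR nulls of 50-55%, 80-85% for 60%, and 75-77% if MR power is only 80%.

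Splitting alpha (0.025 each) would keep the walk claim independent of MR and hold the pair at 1 − 0.975² = 4.94%. However, walk power would fall to 93.0% at n = 50 and 89.9% at 45 evaluable. Reaching 90% would need 46 evaluable, or 46/0.90 = 51.1, rounded up to 52 enrolled. The fixed sequence fits the existing ranking better.
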